ClinicalTrials.gov Document Upload

DOCUMENT DATE (IRB APPROVAL):

23-Feb-2021

NCT NUMBER:

NCT03252522

OFFICIAL STUDY TITLE:

Micronutrients for ADHD in Youth:
The "MADDY" study

INVESTIGATOR NAME:

[name]

ORGANIZATION:

Oregon Health & Science University

Child RCT Protocol 2017

**Protocol for
Micronutrients for ADHD in Youth:
The “MADDY” study
at
Oregon Health & Science University
The Ohio State University/Nationwide Children’s Hospital
University of Lethbridge**

Child RCT Protocol 2017

Aims and Objectives

Aim 1: Replicate acceptability/tolerability of a multi-ingredient micronutrient product for children with ADHD [1].

Hypothesis 1: Consumption of 9-12 capsules, in 3 divided doses daily, of a product containing a blend of vitamins, minerals, amino acids and antioxidants (see Appendix A for ingredients), will be achieved at >80% success, as measured by self-report adherence and pill counts and with no or transient side effects (e.g. nausea, loose stool); and no directly attributable serious adverse events (AEs) (see definition of AE in the section on page 21) recorded via the Pediatric Adverse Events Rating Scale (PAERS).

Aim 2: Determine the prevalence, severity, and effect size for symptoms of irritability and negative mood, which are often associated with ADHD.

Hypothesis 2: Treatment will improve mood, irritability and aggression by a medium effect ($d \geq .50$) [2] as measured by the parent-rated Child & Adolescent Symptom Inventory – 5 (CASI-5), Categories B, C, CD, K, L, Rz, Q, and the child-rated Patient Reported Outcomes Measurement Information System (PROMIS) measures: Depression, Anger, Anxiety, and Peer Relations.

Aim 3: Estimate true effect sizes on ADHD symptoms in this age group, to inform a larger trial.

Hypothesis 3: The micronutrients will reduce participants' ADHD symptoms of inattention and/or hyperactivity/impulsivity, as measured by the parent-rated CASI-5, Question Category A, and the Clinician-rated Clinical Global Impression (CGI) by a medium effect ($d \geq .50$) compared to the placebo [1].

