At the four- and eight-week visits in the RCT and the twelve- and sixteen-week visits in the open label phases, participants will return the pill caddies to the site coordinator with any remaining capsules, to assess adherence. The returned pills will be returned to the research pharmacy, and the pill caddies will be refilled using pills dispensed by the pharmacy or research staff (site dependent) at each in-person assessment. Parents will also be asked to download Medisafe, a pill reminder app and will receive detailed instructions on how to download it and use it.

End-of-RCT, Open Label Extension, and End-of-Trial

At the completion of the 8-week RCT, participants will come in to the research site for an in-person visit at each site to be re-assessed, and assessments repeated (see schedule below in Table 1). Participants will then enter an 8-week open-label extension in which they have the opportunity to knowingly take the active product. The capsules, both active and placebo, will be donated by Hardy Nutritionals, Raymond, Alberta, Canada. Study participants will be eligible to purchase the product,

Child RCT Protocol 2017

DEN, at a price of \$85 per bottle (65% of current retail price) for a person of one year after the completion of the study. At the end of the open label trial (end of month 4, week 16), participants and their parent/guardian, will return to the research lab for a final in person end-of-trial assessment. Questionnaires to be completed are noted below.

Post-study follow up: 30- and 60- and 365-days

Thirty and sixty days following the completion of the open label portion of the study, participants' parents will be contacted by phone to see whether the child participant is still taking the micronutrients. If not, parent/guardian will be asked the questions on the Treatment Cessation questionnaire. In either case, parent/guardian and child will be sent, via REDCap, the assessment questions to complete: e.g. CASI-5, PROMIS measures and others as noted below. At 365-days after study enrollment, participants will be given the opportunity to come in for a visit, as described above, and to provide optional biological samples.

Assessments

ADHD, Emotional and Behavioral Disorder Assessment

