5. **Food Frequency Questionnaire (FFQ):** The children's usual dietary intake captured over 90 days, will be assessed using a standardized, validated VioScreen FFQ, which includes 1,200 food images that users may select, based on branching logic that tracks their choices in food families.
6. **Food Insecurity Measure:** A brief measure asking to what degree the family has experienced food insecurity in the past 12 months, asked at baseline and week 8.

Child RCT Protocol 2017

7. **Parent Target Problems:** (PTP): At baseline, parents will be asked to nominate the child's biggest problem. If the parent cannot select just one, two may be named. The research assistant and parent discuss the named problem and the RA asks questions about the frequency, duration and interference level of the problem. The example field allows the parent to construct a brief narrative of the behavior and its impact on family life. The target symptoms are reviewed and the narratives revised at subsequent visits. A panel of four judges, blind to treatment condition, will independently review the narratives to rate change from baseline on a 9-point scale: 1, normal; 2, markedly improved; 3, definitely improved; 4, equivocally improved; 5, no change; 6, possibly worse; 7, definitely worse; 8, markedly worse; 9, disastrously worse. The mean of the four raters will be compared with primary and key secondary ratings from the original study.
8. **Concomitant treatment measure** will ask parents about any current treatments received (behavioral or physical), for what condition, when started and stopped, and details on dosing or frequency. This measure will be repeated at each in-person visit.
9. **Parent/guardian assessment of the blind** will be reviewed by recording a direct query of whether the parent/guardian believes the child is taking the placebo or the active product, to monitor integrity of the blind.
10. **Treatment acceptability rating** – upon study completion, the parent/guardian will be asked how participating in the study went, any suggestions they have to improve the study, and whether they would recommend the trial to others with symptoms.
11. **Treatment Review** – at 30-, 60- and 365-days post-study, parent/guardian will be asked whether his or her child is still taking the micronutrients and if yes, dosage information. Also parent/guardian will be asked about any other treatments used or obtained in the time period since last interviewed.

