12. **Treatment cessation** – at 30-, 60- and 365-days post-study, parent/guardian will be asked whether his or her child is still taking the micronutrients. If not, the parent/guardian will complete this measure to report on the reasons for stopping the treatment.
13. **(Optional) Qualitative assessment** – a smaller sample of participants will be asked whether they want to provide optional qualitative input regarding the study. The scripted, phone-based interview, will be completed a member of the study staff who will conduct all the interviews. See details of the qualitative assessment in separate document, included as part of IRB submission.

For this qualitative component, interviews with parents of children enrolled in the clinical trial will be asked about their perspectives and experience of using medications and the micronutrients. Questions will address the following concept domains and questions:

- a. Current and past treatments/therapies used – what are the perceived benefits and limitations?
- b. Reasons for micronutrients – what are the perceived benefits? What are the facilitators and barriers to micronutrients as a treatment option; e.g. adherence and tolerance (# capsules/day), swallowing difficulties, side effects, cost, practitioner knowledge
- c. Accessibility –how would micronutrients incorporated into part of healthcare services? E.g. after nothing else has worked, or be the first step in treatment?

Child RCT Protocol 2017

- d. Patient oriented outcomes – what is important for parents/patients to find out from the research? What would be impactful for them?

Methodology

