3. **Child Target Problem-** At baseline, child will be asked to nominate his or her biggest problem or symptom. If the child cannot select just one, two may be named. The research assistant and child discuss the named problem and the RA asks questions about the frequency, duration and interference level of the problem. The example field allows for the construction of a brief narrative of the behavior and its impact on family life. The target symptoms are reviewed and the narratives revised at subsequent visits. A panel of four judges, blind to treatment condition, will independently review the narratives to rate change from baseline on a 9-point scale: 1, normal; 2, markedly improved; 3, definitely improved; 4, equivocally improved; 5, no change; 6, possibly worse; 7, definitely worse; 8, markedly worse; 9, disastrously worse. The mean of the four raters will be compared with primary and key secondary ratings from the original study.
4. **Treatment Acceptability**– upon study completion, the child participant will be asked for their opinion on participation and any suggestions they have to improve the study, and whether they would recommend the trial to others with symptoms.

In person at the end of the RCT

5. **Child assessment of the blind** will be captured by asking the youth whether they believe they are taking the placebo or real product.

Teacher or Other Adult-rated measures

Completed at baseline and 8 week RCT, 16-week end-of-study – time: 10 minutes:

1. **CASI-5** selected subscales (3 eligibility subscales and peer relationships) will used at baseline and to monitor the effectiveness of the child’s response to intervention at two other time points.

Data and Specimens

Blood, hair, saliva, urine, and feces collection

Collected at baseline, 8 weeks and week 16 (end-of-study) – time: 5-10 minutes

Blood collection

Per FDA requirements, participants will be **required** to provide blood samples at each in-person visit. These samples will be used for safety measures and for research purposes. Analysis will include CBC, TSH, iron, a number of supplemented nutrients including B vitamins and Vit D, and

Child RCT Protocol 2017

blood for future analysis of targeted and untargeted metabolomics and IL-6 and TNF-a. Total blood collection will be approximately 18ml, or 3 teaspoons. See “Blood Sample Collection Info for OHSU” chart included in IRB submission, for details.

Hair Collection

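### Children who stop in weeks 0 to 16 have no reasons form scheduled at the time of stopping, and acceptability is first rated at week 16, after open-label exposure

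*Combined protocol and SAP*

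**What the plan says.** The first aim is stated as "Aim 1: Replicate acceptability/tolerability of a multi-ingredient micronutrient product for children with ADHD". Hypothesis 1 (Aims and Objectives) measures it by reported adherence, capsule counts, side effects and serious adverse events recorded on the PAERS, with a success target above 80% for consumption.

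Reasons for stopping appear in Parent/guardian-rated measures, item 12 (Treatment cessation): "at 30-, 60- and 365-days post-study, parent/guardian will be asked whether his or her child is still taking the micronutrients". The next sentence reads "If not, the parent/guardian will complete this measure to report on the reasons for stopping the treatment". Post-study follow up fixes the two earlier contacts: "Thirty and sixty days following the completion of the open label portion of the study, participants' parents will be contacted by phone". That section, the Design Overview and the footnote to the measures table count the 365 days from enrollment; item 12 counts them from the end of the study. Table 1 marks the form only in the follow-up columns.

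Acceptability is asked once. For the parent (item 10): "upon study completion, the parent/guardian will be asked how participating in the study went". For the child (Child-rated measures, item 4): "upon study completion, the child participant will be asked for their opinion on participation". Table 1 marks both at week 16 only and labels the child's version as trial feedback. By week 16 all continuing children, including those randomized to placebo, have been offered open-label active product for eight weeks.

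**The concern.** Families who stop early are those with most to say about whether the capsules were acceptable. Under this schedule, nothing asks them when they stop. Capsule counts show how much was taken, and the PAERS shows which events occurred. Neither shows that a family stopped because of the number of capsules or because they saw no benefit.

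Two features of the plan make the reason more useful.

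- Children can leave for causes unrelated to the product. The payment text after Setting and Recruitment methods discontinues a child who declines the questionnaires. That text and Baseline Assessment imply that refusing a required blood sample can also end participation. Lethbridge takes no blood, so causes of leaving may differ by site.
- Data Analysis carries the last observation forward for children who do not complete eight weeks. How plausible that is depends on why they left, in each arm.

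**Working it through.** No figure in the plan decides this point. The check sets the schedule against Aim 1 and counts who is affected.

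1. **Aim 1's declared measures.** Capsules are counted at weeks 4, 8, 12 and 16 (Adherence). The PAERS is marked at baseline, weeks 1, 4, 8, 12 and 16, and follow-up (Table 1). A child who stops in week 3 already has baseline and week-1 PAERS data. These measures can be compared by arm, although Data Analysis specifies no Aim 1 analysis.

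2. **Reasons form.** Table 1 has no mark at weeks 4, 8, 12 or 16 and none at withdrawal. Its lead question, whether the child still takes the micronutrients, does not fit a child on blinded capsules that may be placebo.

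3. **Recall delay.** Assume capsules start at enrollment (day 0) and the child stops on day 21. Week 16 is day 16 × 7 = 112.
   - 30-day call: 112 + 30 = 142, a gap of 142 − 21 = 121 days.
   - 60-day call: 112 + 60 = 172, a gap of 172 − 21 = 151 days.
   - 365-day contact from enrollment: 365 − 21 = 344 days, about 11 months.

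   The first two calls are timed from completing open label, so a child who has left has no date from which to count them. Only the 365-day contact is independent of completion.

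4. **Other routes.** Risk assessment and right to withdraw keeps children with an exclusion violation under observation for the planned duration, and promises follow-up of any discontinued child without naming an instrument or time. The Data Safety Monitoring Plan asks withdrawing families for permission to keep questionnaire follow-up. The only other rule found for recording a reason (Consent and Assent) covers families who do not enroll.

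5. **Acceptability.** Ratings scheduled before open-label product: 0 of 135. Week-16 ratings could be split by original arm, but both arms have by then been offered active product.

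6. **Numbers affected.** Two dropouts per arm per site gives 2 × 2 × 3 = 12, and 135 − 12 = 123, as the plan states. At 3:2 the arms are 81 and 54, so 6/81 = 7.4% active and 6/54 = 11.1% placebo. Exact 95% intervals are 2.8% to 15.4% and 4.2% to 22.6%. Numbers this small support description by arm, not a test.

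**The case against.** The strongest reply is that no stated hypothesis depends on these forms. Hypothesis 1 names neither of them and sets a fixed target with no placebo comparison. Its own measures are collected by arm in the blinded phase, and the DSMB looks at safety differences between arms. This stands, and it limits the point to a modest improvement.

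A reader might infer that Aim 1 receives no scheduled data from children who stop, or that its randomized contrast is lost. The documents support neither. Adherence and PAERS data accrue up to stopping and can be compared by arm. What is missing is the stated reason at the time and the opinion before open label.

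Other replies stand in part:

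- The 365-day contact and the promised follow-ups could recover some reasons. They are late, or name no instrument.
- The week-1 call and later contacts take reports of side effects and swallowing for dose decisions, and optional interviews ask about capsule number. The first is not a record of why a child stopped; the second covers a smaller sample.
- Active and placebo are tabulated at the same 9 and 12 capsules, so an arm comparison says little about capsule burden. It can still describe side effects and perceived lack of benefit as reasons for stopping.
- The acceptability form asks about the trial and not the product. Bringing it forward unchanged would not measure acceptability of the capsules.

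**Conclusion.** The point holds as a gap in timing. During weeks 0 to 16 no reasons form is scheduled when a child stops, and no acceptability rating precedes open-label exposure. The ratings will come mainly from children who stayed, and they offer no comparison with placebo.

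The plan's own allowance is 12 dropouts of 135, or 8.9%. This is only a guide to the number affected. The sample-size paragraph does not say whether 123 means retained to week 8 or week 16, and a dropout need not be a child who stopped because of the capsules.

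The size of any bias in the ratings cannot be calculated: the documents give no expected rating and no scoring for the form. A reader might set such ratings against the 80% target, but that target concerns consumption.

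The conclusion rests on the schedule as printed. Part of the text under Setting and Recruitment methods, and the text under Cross Site Coordination, were not available for this check. The change is a cheap improvement and not a threat to the trial's stated hypotheses.

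**What to change.** - Trigger the existing cessation form whenever a child permanently stops capsules in weeks 0 to 16. Word it for blinded study capsules and record the date of stopping.
- Give the parent and child acceptability forms at that point, and to all children at week 8 before open-label product is dispensed. The week-8 visit already carries the question about the blind.
- Add one item on acceptability of the capsules themselves.
- Keep the week-16 forms.
- Report reasons for stopping and week-8 acceptability descriptively by randomized arm, keep stoppers in the denominator, and state how many could not be reached.
- Reconcile whether the 365-day contact runs from enrollment or from the end of the study.

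Cost: extra marks in Table 1, a REDCap trigger and an amendment at each site. The measures table gives 1 minute for the cessation form and 2 for the parent acceptability form. It gives no time for the child's form; assuming 2 minutes, the burden is 2 + 2 = 4 minutes at week 8 and 1 + 2 + 2 = 5 minutes at stopping, plus the added item. Reported acceptability may come out slightly lower. Sample size and randomization are unchanged.

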Phone screen data, including inclusion/exclusion criteria, and the CASI-5 responses will be reviewed and discussed by the study PIs and the research assistant. Any questions or concerns regarding enrollment, based on information provided by the parent/guardian or participant, may be handled with phone or in-person consultation with an onsite study physician. If necessary, the consultation or meeting enables a brief review of medical history and the opportunity to identify any potential concerns prior to enrollment.

Consent and Assent

After eligibility is established based on phone screen and CASI-5 responses, and review of medical records and/or site physician assessment, if necessary, the parent/guardian and child will be invited to meet with a research staff team member for a baseline visit, in designated office space at one of the three sites to discuss the study and to complete consent and assent prior to any study procedures. Prior to the first visit, the consent and assent forms will be sent to the parent/guardian for review in before the first meeting. This will facilitate the parent's ability to formulate and ask questions in advance of the first visit. The consent will be signed onsite, using REDCap.

As this study represents minimal risk to the child and offers potential benefit, the consent of one parent/guardian will be sufficient for participation. The child will be provided with information about the study using simple language that is appropriate for a child as young as 6 years of age. The child will be clearly told that s/he does not have to participate, s/he can change his/her mind at a later time. Provided that both the parent/guardian and child want to participate, both will provide electronic consent/assent via the secure, HIPAA-compliant REDCap web portal. Documentation of assent/consent, via an electronic signature, will be captured for each participant and parent/guardian. If the parent/guardian or child does not consent/assent or is excluded for any other reason, data already collected will be retained for the purpose of characterizing those who made contact. The reason for not enrolling will be noted in REDCap. Parents will be asked whether they are interested in communicating regarding the MADDY research study via text. A separate consent form will be provided and the text communication explained.

Procedures

Baseline Assessment

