Once consent and assent are given, the parent/guardian and child will complete the other baseline questionnaires electronically, also via the REDCap web portal. Details regarding the measures are noted in the section below (starting on page 13). Participant will also have weight, height and blood pressure measures taken and recorded electronically in the REDCap portal. Any paper-collected ratings data will be entered weekly.

Child RCT Protocol 2017

Blood, hair, saliva, and urine samples will also be collected from the child participant at the baseline assessment, along with the stool sample, if possible. If the child cannot give a stool sample at the baseline visit, the parent will be given the collection kit and instructed to collect the sample later that day or the next morning, before the child begins taking the capsules. The samples will be stored as below, in order to examine nutrient levels, systemic inflammation, DNA methylation, metabolomics and microbiome markers. Except for the blood sample at baseline and week 8, the child will not be excluded from the study without providing any one, or all, of the biological samples (hair, saliva, urine or feces). Child-appropriate information sheets will be provided to the participants to explain the biological sample collection and receipt of parent/guardian consent and child assent will be documented. Aside from blood, which will be collected and stored per laboratory requirements, samples that are collected will be entered on a paper study sample log, by site (A1 A=Oregon, sample 1, saliva; etc), along with the participants ID number. For stool and hair, a record of the serial number of the collection container will be added to participant's REDCap record. Hair and urine collection will be noted in participants' REDCap record.

Blood pressure, heart rate, height and weight will also be assessed at in-person visits by a trained research assistant using instruments calibrated according to hospital maintenance schedule. Participants will be asked to complete the VioScreen version of the Food Frequency Questionnaire (FFQ) at baseline and at the end of eight weeks with input from one parent/guardian.

Enrollment

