At least 20 strands of hair, approximately the diameter of a pencil lead will be cut close to the root from the posterior aspect of the head. The hair will be tied at the cut end to identify the most recent portion of hair growth. Samples will be wrapped in static free paper, zip-locked, placed in a light occlusive envelope, labeled with participant’s study identification only and stored at the individual lab sites until all hair is collected. Then it will be shipped to OHSU for analyzes.

Saliva collection

Using the Oragene – DNA, OG-600 collection kit, participants will be asked to provide saliva samples during their visits at: baseline, 8 weeks, 16 weeks, in order for us to begin to understand the effect that micronutrient treatment might have on DNA methylation. They will be provided with instructions on how to spit into the collection tube and seal up the kit, which will be labelled with the participant’s ID number and recorded on a log, then stored in the lab, in a specially labelled and locked file drawer and/or the Clinical Research Center, until all samples are collected from participants. The specimens collected at the other two sites will be stored at their onsite location. Once the study finishes, and all samples have been collected, the saliva samples will be sent to the lab determined most appropriate for analyses, once funding is available.

Stool sample collection

Participants will be asked to provide three stool samples, collected in the home setting, within 48 hours of an in-person study visit, using the OMNIgene Gut OMR-200 collection kit: at baseline, end of RCT (8 weeks) and end of open label (16 weeks); in order for us to begin to understand the effect that micronutrient treatment might have on the microbiome. These data are exploratory components of the study and seen as a pilot investigation because this is a very new area and there is little scientific literature to direct these analyses. However, a series of studies have now documented the impact of the gut microbiome on behavioral disorders such as autism, anxiety, and depression directly and indirectly. See [51] for an example. The purpose of collecting the samples for storage is to identify the relationship between the gut microbiome and clinical symptoms of ADHD at a later date, once funds are available to generate and analyze the samples.

Procedures for stool sample collection

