Participants will be asked if they would be willing to provide a stool specimen. If they agree, they will be mailed a stool specimen collection kit and instructions, to be performed ideally within 24-48 hours of their next visit. This kit includes a swab system and sterile tube for collection of stool material from tissue wipe after defecation, as well as a biohazard bag and brown paper bag for transportation. After defecation at home, the subject or parent will wipe the provided swab on the toilet paper to collect the stool specimen to be put in the tube. The swab will then be thrown away, and the tube sealed and brought to the research assistant at the participant’s next visit. If the participant is not returning for another visit, the participant will be given a mailer and instructions on

Child RCT Protocol 2017

how to mail the sample back. After being delivered to the lab, the specimen will be frozen at -80 C until further processing, once funding is available. In Oregon, freezer space in the Core Lab run by [name], will be used to store the samples. Stool sample collection and storage will be identical at the other two sites per best practice recommendations [52]. University of Lethbridge will ship their samples to OHSU for storage; Ohio State will store their samples locally until sample generation and analyses funds are available.

Urine sample collection

Participants will be asked to provide three urine samples, collected in the home setting or at the lab, first thing in the morning: at baseline, end of RCT (8 weeks) and end of open label (16 weeks) in order for us to begin to understand how metabolism of the micronutrients might impact response to treatment. Participants will be given a sterile urine specimen collection container and instructed to fill it at least half full (a minimum of 4ml). If done at home, participant will store urine in the refrigerator until lab appointment. The urine samples will be frozen at -80 C, in the Core Lab run by [name], until further processing, pending available funds.

Sharing of Results

Due to the exploratory nature of this research and the time delay from collection to generation and analyzation of the samples, results from the biological samples will not necessarily be shared with participants' families.

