However, once samples are analyzed, participants may be re-contacted, even if they have completed the study, if any safety concerns arise from the analyses. Participants will be asked whether they want to know the results. As the collected samples may or may not be analyzed by a CLIA-approved lab the reliability of the results may not be unknown. Participants will be advised to run further analyses, at their own expense. The risks associated with receiving this information include, but are not limited to: costs of additional medical care and testing, impact on insurability, and psychological risks, if you receive information that is upsetting.

Specimen Banking and Repository

As noted in each section pertaining to the biological samples, specimens will be stored (at each of the three sites, unless specified) for future generation and analyses, which will occur once sufficient funding is available. Specimens may be accessed by any of the named PIs or their representative. Permission via an email granting access will be sufficient. Study-generated identification (coded) information will be provided with the specimens so that the data may be matched up by treatment arm. Data and samples from this study may be shared with other study investigators at Ohio State or University of Lethbridge for future research studies. A code number is assigned to each child, their cells and genetic information, as well as to information about them. Only the investigators and people involved in the conduct of the study will be authorized to link the code number to the participant. Other investigators or outside labs, including ZRT Laboratory, who receive samples, saliva/genetic information/other data for research, will be given only the code number, but not identifying information.

Child RCT Protocol 2017

ZRT Laboratory in Beaverton, Oregon, will be analyzing approximately .5-1ml of blood and up to 2 mls of urine for neurotransmitters, diurnal analytes, sex steroids, hormones and mineral. All samples will be de-identified. _

Data Analysis

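### Baseline stool collected at home after the visit has no prompt return route: as written, the tube waits about four weeks before freezing, against roughly two days or less for other stool samples

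*Combined protocol and SAP*

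**What the plan says.** The protocol covers stool in three places.

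- **Baseline Assessment.** Stool is taken at the visit if the child can provide it. Otherwise the parent receives the kit and is "instructed to collect the sample later that day or the next morning, before the child begins taking the capsules".
- **Stool sample collection.** Samples at baseline, week 8 and week 16 are to be "collected in the home setting, within 48 hours of an in-person study visit".
- **Procedures for stool sample collection.** For families who agree, "they will be mailed a stool specimen collection kit and instructions, to be performed ideally within 24-48 hours of their next visit". The sealed tube is handed to the research assistant at the next visit. The one other route is conditional: "If the participant is not returning for another visit, the participant will be given a mailer". Freezing at -80 C follows delivery to the lab. No home storage condition is given.

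Design Overview and Table 1 place the in-person visits at baseline and weeks 4, 8, 12 and 16. Under Consent and Assent, families come to the baseline visit "to complete consent and assent prior to any study procedures", and consent is signed on site.

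For specimen records, Baseline Assessment lists a site-coded log, the participant ID and the container serial number. It lists no collection or freezing date.

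For urine, the Urine sample collection section asks for three samples "collected in the home setting or at the lab, first thing in the morning", while Baseline Assessment says "urine samples will also be collected from the child participant at the baseline assessment". The paragraph on participant payments states that the Canadian site collects no urine.

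**The concern.** The return rule was written for a kit used just before a visit, which fits weeks 8 and 16. The home-collected baseline sample comes just after a visit, so the same rule produces a long wait. Baseline is the reference for every later comparison, and it cannot be recollected once the capsules have started.

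Aim 4 looks for nutrient biomarkers of mechanism both within and between participants. If baseline tubes sit unfrozen for weeks and later ones for a day or two, a change in the microbiome between baseline and week 8 or 16 could come from storage, from treatment, or from both. Baseline is also mixed within itself, because some children hand over a sample at the visit and others about four weeks later. With no dates among the listed specimen fields, a later analyst of the banked samples could not count on being able to adjust for hold time.

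**Working it through.** The plan states no figure for hold time, so there is none to reproduce. It follows from the schedule.

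**Hold time = day of handover minus day of collection** (baseline visit = day 0)

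| Sample | Collected | Handed over | Held before freezing |
|---|---|---|---|
| Baseline, given at the visit | day 0 | day 0 | about 0 days |
| Baseline, collected at home | day 0 to 1 | next visit, week 4: 4 × 7 = day 28 | 28 - 1 = 27 to 28 - 0 = 28 days |
| Weeks 8 and 16 | up to 48 hours before the visit | that visit | about 0 to 2 days |

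The gap between home-collected baseline samples and week-8 or week-16 samples runs from 27 - 2 = 25 to 28 - 0 = 28 days. The last row assumes collection ahead of the visit, as the stool procedures envisage. The 24-48 hour target there is an ideal, and the 48-hour window does not say before or after.

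**Which comparisons are exposed.** Let a fraction q of children collect baseline stool at home, and let the long hold shift the measured value by h standard deviations (SD). With no true treatment effect, the expected change from baseline is -q × h in each arm. The difference between arms is (-q × h) - (-q × h) = 0, because both arms follow the same rules and the baseline sample precedes the first capsule.

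A simulation illustrates this. Everything in it except the arm sizes is assumed: 135 children at 3:2 (135 × 3/5 = 81 and 135 × 2/5 = 54), true effect 0, within-child correlation 0.5, h of 0.25 or 0.5, q from 0.5 to 1, and 4,000 repetitions per setting. The between-arm test was on the difference in change.

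| Comparison | Bias | Rejections at nominal 5% |
|---|---|---|
| Change within the active arm | -0.13 to -0.50 SD | 21% to over 99% |
| Active minus placebo difference in change | 0.00 SD | 4.6% to 5.3% |

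These figures show the direction and which contrast is exposed. They are not estimates for this trial, because nothing in the documents fixes q or h.

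**Week 16.** After week 8 all children enter the open-label extension, so no concurrent placebo group remains to cancel the shift.

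**Handling standard.** The reference cited for stool collection and storage is, in the reference list, a particle-physics paper. That is a citation slip and says nothing about the kit, but it leaves the documents with no stated limit on time before freezing.

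**The case against.** The strongest reply is that the four-week wait is inferred. The next-visit instruction belongs to a mailed kit, whereas the baseline kit is handed over at the visit, so the return rule may not have been meant for it. That is fair about intent, but it does not close the gap. Either the rule applies and the tube waits until week 4, or it does not apply and the baseline sample has no return route at all.

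Several stronger readings are tempting, and the documents do not support them.

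- **The home rules ignore baseline.** A reader might infer this from the stool procedures alone. Baseline Assessment does give an in-visit option and a collection time that fits the 48-hour window. What is missing is return and storage.
- **The treatment comparison is biased.** It is not, as the working shows. Uneven hold times could add noise to baseline and so cost precision. The ANCOVA under Data Analysis is tied to the CASI-5 and CGI, and no stool analysis is specified, so that cost cannot be given a number.
- **Baseline urine is taken before consent.** A home first-morning sample brought to the baseline visit would precede on-site consent. But Baseline Assessment places urine at the visit after consent, and the urine section also allows collection at the lab. The tension concerns one option at two sites, at most 2 × 45 = 90 children.
- **First-morning urine should be dropped.** That would let time of day vary at every time point, which is a trade-off and no clear gain.
- **The plan promises a diurnal pattern.** The banking section lists urine "of urine for neurotransmitters, diurnal analytes, sex steroids, hormones and mineral". This names a class of analytes and commits to no within-day profile.

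It also stands that stool is voluntary, that the protocol calls the stool data exploratory and a pilot, and that no primary outcome depends on either specimen.

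**Conclusion.** The point holds for stool, in a limited form. Following the text, a baseline sample collected at home is held 27 to 28 days before freezing, under unstated conditions, against about 0 to 2 days for the others. Within-child change from baseline, and the open-label week-16 change in particular, could carry a storage effect that cannot be separated from time on treatment. The randomized week-8 contrast stays unbiased, with a possible loss of precision.

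The size of any storage effect is unknown. It depends on how many children collect at home and on how stable the named kit is when unfrozen, and the documents give neither. If the kit keeps well for four weeks, the practical effect could be small. The trial's main conclusions are not affected. The change is still worth making, because it is cheap and a baseline sample cannot be replaced.

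For urine, only a clarification is needed.

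**What to change.** **Stool.** In Baseline Assessment and in Procedures for stool sample collection, state that every baseline kit taken home comes with a mailer, or with a prompt drop-off arrangement, and that the sample is sent within 48 hours of collection. State the storage condition until then. Log the collection date and the freezing date for every stool sample at all time points, so that hold time can be adjusted for or examined in a sensitivity analysis.

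**Urine, two US sites.** State that baseline urine is collected after consent, as Baseline Assessment already implies. Record place and clock time at each collection. Keep first-morning collection.

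**Cost.** One mailer per take-home baseline kit (the plan already supplies mailers in some cases), two logged dates per stool sample, a place and a clock time per urine sample, and a few lines of protocol text. Some difference remains between postal transit at baseline and hand delivery later. The logged dates would show how large it is.
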